3.7.2 Off Study Criteria

All patients will be followed for overall survival, when possible.

Patients who discontinue treatment due to progression will be followed for survival every 3 months.

Patients who come off therapy for reasons other than progression should be followed until progression or institution of new anti-tumor therapy. They should then be followed for survival.

3.7.3 Off Study Procedure

Authorized staff must notify Central Registration Office (CRO) when a subject is taken offstudy. An off-study form from the web site

(http://home.ccr.cancer.gov/intra/eligibility/welcome.htm) main page must be completed and faxed to [contact].

All subjects must be registered through the NCI Central Registration Office (CRO). An off-study form will be supplied by the Coordinating Center, NCI CCR. Send the completed off-study form to the Coordinating Center's Research Nurse; [name]; [contact], [contact].

^k Complete Neurologic exam will be performed prior to every evaluation where an MRI is scheduled.

Version Date: 07/17/2025 Page 30 of 96

4 CONCOMITANT MEDICATIONS/MEASURES

4.1 G-CSF ADMINISTRATION

4.1.1.1 If neutrophil count < 1500/mm³ or platelet count < 75,000/mm³, hold topotecan until counts resolve to < grade 2 CTC grade toxicity. If neutrophil count remains < 1500/mm³ x 1 week or more, granulocyte colony stimulating factor may be used to support. If neutrophil count achieves level > 1500/mm³, patient may resume treatment with oral topotecan. If toxicities do not resolve to < CTC grade 2 after 3 weeks of drug hold, and with G-CSF support patient must be removed from study. Platelet counts that do not resolve to < CTC grade 2 after 3 weeks require removal of patient from study.

4.2 CORTICOSTEROIDS

Corticosteroids should be used in the smallest dose to control symptoms of cerebral edema and mass effect, and discontinued if possible. Patients must not be on a dexamethasone dose of greater than 16 mg/day.

4.3 ANTI-SEIZURE MEDICATIONS

Anti-seizure medications should be used as indicated. If for unavoidable clinical reasons (severe allergies, toxicities, etc.) a patients AED is switched to the alternate AED group the following guidelines must be followed:

- 4.3.1.1 Patients are to be maintained on non-EIAEDS
 - 4.3.1.1.1 Patients who were previously on an EIAED and need to change anticonvulsants, should first be started on a non-EIAED. Two weeks washout after this change are required before starting treatment on study.
 - 4.3.1.1.2 Patients who were previously on a non- EIAED and were inadvertently and temporarily changed to an EIAED, should immediately be started on another non-EIAED. The patient may continue the current treatment dose while a non- EIAED is restarted.
- 4.3.1.2 Patients who were previously on a non-EIAED and need to permanently change anticonvulsant, but who cannot change to another non-EIAED need to be removed from the study due to drug-drug interactions
- 4.3.1.3 Patients who were previously on a non-EIAED and need to change anticonvulsants, should be started on another non-EIAED if at all possible. No delays in treatment would be required.

4.4 FEBRILE NEUTROPENIA

Febrile neutropenia may be managed according to the local institution's Infectious Disease Guidelines. Measures may include appropriate laboratory testing, including blood and urine cultures and the institution of broad-spectrum antibiotics. If a source for the fever is not

Version Date: 07/17/2025 Page 31 of 96

identified or the fever resolves when the neutrophil count recovers, antibiotics may be discontinued and the patient observed.

4.5 **ANTI-EMETICS**

The use of anti-emetics will be left to the investigators' discretion.

4.6 OTHER CONCOMITANT MEDICATIONS

Therapies considered necessary for the well-being of the patient may be given at the discretion of the investigator. Other concomitant medications should be avoided except for analgesics, chronic treatments for concomitant medical conditions, or agents required for life-threatening medical problems. All concomitant medications must be recorded. For patients with known hypertension on BP medications, strict compliance with treatment should be reinforced.

4.7 OTHER ANTICANCER OR EXPERIMENTAL THERAPIES

No other anticancer therapy (including chemotherapy, radiation, hormonal treatment or immunotherapy) of any kind is permitted during the study period. No other drug under investigation may be used concomitantly with the study drug.

4.8 SURGERY

If neurosurgical management is required for reasons not due to tumor progression, these procedures must be documented, including the indications for surgery, the surgical operative note and pathology report. If possible defer surgery for 4 weeks from last dose of therapy. Patients who undergo resection for presumed tumor progression but are shown to only have treatment associated changes (treatment effect or necrosis) can resume treatment once they have recovered from the surgical procedure. Pazopanib treatment can only resume > 28 days after surgery.

5 BIOSPECIMEN COLLECTION

5.1 PATHOLOGY REVIEW

Following registration, slides from the most recent pre-registration biopsy must be submitted for review. The purpose of this review is to verify the histologic diagnosis.

The materials are to be submitted after registration step 1 to:

[name] Toronto General Hospital [name] [contact]

Pathology Materials Required for Review:

- 1. One to two representative H&E stained slides from a pre-registration biopsy demonstrating lesion.
- 2. A copy of the pathology report and the operative report.
- 3. The Tissue Collection Shipping Form (see 15.3).
- 4. The submitting institution is responsible for the costs of shipping and handling.

Version Date: 07/17/2025 Page 32 of 96

6 DATA COLLECTION AND EVALUATION

6.1 DATA COLLECTION

The PI will be responsible for overseeing entry of data into an in-house password protected electronic system (C3D) and ensuring data accuracy, consistency and timeliness. The principal investigator, associate investigators/research nurses and/or a contracted data manager will assist with the data management efforts. All data obtained during the conduct of the protocol will be kept in secure network drives or in approved alternative sites that comply with NIH security standards. Primary and final analyzed data will have identifiers so that research data can be attributed to an individual human subject participant.. Designated research staff from the registering institution will enter the data via remote electronic data entry. The protocol specific electronic forms are to be used by the participating sites. All investigators will utilize these forms for Baseline, Treatment, Adverse Events, Tumor Evaluation, Off Treatment, Survival, and Off-study data.

All data will be kept secure. Personal identifiers will not be used when collecting and storing data. An enrollment log will be maintained in the regulatory binder/file which is the only location of personal identifiers with unique subject identification number.

End of study procedures: Data will be stored according to HHS, FDA regulations, and NIH Intramural Records Retention Schedule as applicable.

Loss or destruction of data: Should we become aware that a major breach in our plan to protect subject confidentiality and trial data has occurred, this will be reported expeditiously per requirements in section 7.2.1.

6.1.1 Source Documentation Timeframes

The following information will be entered into C3D within the indicated timeframes. In addition, the source documents should be provided to the NCI BTTC coordinating center research nurse within the indicated timeframe.

Data Set / Source Documents	Schedule for Submission
Regulatory Documents (as described in the BTTC Operations Manual)	Prior to Patient Registration
Eligibility Checklist	Prior to Patient Registration
Copy of signed & dated Informed Consent w/ HIPAA Authorization	Prior to Patient Registration
Pathology Report (from the most recent pre- registration diagnostic biopsy or surgery)	Prior to registration
Baseline Data (To include prior disease/treatment history, and baseline clinical evaluation information)	Within 14 days after the registration date
Baseline MDASI – BT Questionnaire	Within 14 days after the registration date
Baseline Source Documents	Within 14 days after the registration date

Version Date: 07/17/2025 Page 33 of 96

6.1.2 Database Entry Timeframes

The following data should be entered into C3D within the specified timeframes. Source documentation will be kept at the participating site.

Treatment (Cycle) Data (To include treatment, response, AE, and clinical evaluation information)	Within 40 days after the first day of each treatment cycle.
Off Treatment Data	Within 10 days after the last date of any modality of protocol treatment.
Follow-up (Survival) Data	Within 52 days after the last treatment date and then every 90 days until Off Study (unless otherwise specified by the protocol).
Non-Treatment Data (May include Quality of Life questionnaires (MDASI-BT), Specimen Tracking information, Pathology Specimen Submission, etc.)	Within 10 days after each scheduled assessment, event, or activity.
Off Study Data	Within 10 days after the date the patient is removed from the study.

6.1.3 Confidentiality

All documents, investigative reports, or information relating to the patient are strictly confidential. Any patient specific reports (i.e. Pathology Reports, MRI Reports, Operative Reports, etc.) submitted to the NCI BTTC Coordinating Center must have the patient's full name & social security number "blacked out" and the assigned patient ID number and protocol number written in. Patient initials may be included or retained for cross verification of identification.

6.1.4 Safety Data

All patients receiving study agents will be evaluated for safety. The safety parameters include all laboratory tests and hematological abnormalities, CNS observations, physical examination findings, and spontaneous reports of adverse events reported to the investigator by patients. All toxicities encountered during the study will be evaluated according to the NCI Common Terminology Criteria for Adverse Events (CTCAE) version 4.0 and recorded prior to each course of therapy. Life-threatening toxicities that are unexpected and assessed to be possibly related to the study agent/s should be reported immediately as per section 7.2.

Information about all adverse events, whether volunteered by the subject, discovered by investigator questioning, or detected through physical examination, laboratory test or other means, will be collected and recorded on the Adverse Event Case Report Form and followed as appropriate. An adverse event is any undesirable sign, symptom or medical condition occurring after starting study drug (or therapy) even if the event is not considered to be related to study drug.

Version Date: 07/17/2025 Page 34 of 96

Medical conditions/diseases present before starting study treatment are only considered adverse events if they worsen after starting study treatment (any procedures specified in the protocol). Adverse events occurring before starting study treatment but after signing the informed consent form are recorded on the Baseline Evaluations Case Report Form. Abnormal laboratory values or test results constitute adverse events only if they induce clinical signs or symptoms or require therapy, and are also recorded on the Adverse Events Case Report Form.

6.1.5 Data Sharing with Pharmaceutical Collaborator, Novartis

NCI may share data from this study with its pharmaceutical collaborator, Novartis, pursuant to the NCI CDA with Novartis. Specifically, Novartis may access and review analytical results and primary quantitative and empirical data including identifiable private information in accordance with the terms of the CDA.

6.2 **DATA MONITORING**

All submitted data will be monitored by the BTTC Protocol Manager specifically assigned to this protocol. Requests for correction of data deficiencies will be sent via mail to the Institutional Coordinator. Any major deficiencies will be corrected by telephone communication. All data will be monitored for completeness. Key parameters such as drug dosages including attenuations and escalations, toxicity documentation and tumor measurements will be analyzed. All data deficiencies will be corrected within two weeks.

6.3 DATA SHARING PLAN

6.3.1 Human Data Sharing Plan

What data will be shared?

I will share human data generated in this research for future research as follows (check all that apply):

X Coded, Linked data in an NIH-funded or approved public repository.
Coded, Linked data in another public repository.
X Identified data in BTRIS (automatic for activities in the Clinical Center)
X Identified or coded, linked data with approved outside collaborators under appropriate agreements.
I will not share human data generated in this research for future research. If checked, explain:
How and where will the data be shared?
Data will be shared through (check all that apply):
X An NIH-funded or approved public repository. Insert name or names: clinicaltrials.gov
Another public repository. Insert name or names:
X BTRIS (automatic for activities in the Clinical Center)

X Approved outside collaborators under appropriate individual agreements.

Version Date: 07/17/2025 Page 35 of 96

X Publication and/or public presentations.

When will the data be shared? (check all that apply)

X Before publication.

 \underline{X} At the time of publication or shortly thereafter.

6.4 RESPONSE CRITERIA

The primary efficacy endpoint is progression free survival (PFS) at six months from patient registration for bevacizumab naïve patients and PFS at 3 months for patients with prior bevacizumab treatment. However, objective response status should be measured and recorded.

6.4.1 Definitions of Response

- 6.4.1.1 Measurable Disease: Bidimensionally measurable lesions with clearly defined margins by CT or MRI scan.
- 6.4.1.2 Evaluable Disease: Unidimensionally measurable lesions, masses with margins not clearly defined.
- 6.4.1.3 Non-Evaluable Disease: Not Applicable for response evaluation
- 6.4.1.4 Objective Status, To Be Recorded at Each Evaluation: If there are too many measurable lesions to measure at each evaluation, choose the largest two to be followed before a patient is entered on study. The remaining lesions will be considered evaluable for the purpose of objective status determination. Unless progression is observed, objective status can only be determined when ALL measurable and evaluable sites and lesions are assessed.
 - 6.4.1.4.1 Complete Response (CR): Complete disappearance of all measurable and evaluable disease. No new lesions. No evidence of non-evaluable disease. All measurable, evaluable and non-evaluable lesions and sites must be assessed using the same techniques as baseline. Patients must be on no steroids.
 - 6.4.1.4.2 Partial Response (PR): Greater than or equal to 50% decrease under baseline in the sum of products of perpendicular diameters of all measurable lesions. No progression of evaluable disease. No new lesions. All measurable and evaluable lesions and sites must be assessed using the same techniques as baseline. The steroid dose at the time of the scan evaluation should be no greater than the maximum dose used in the first 8 weeks from initiation of therapy.
 - 6.4.1.4.3 Partial Response, Non-Measurable (PRNM): Not applicable.
 - 6.4.1.4.4 Stable/No Response: Does not qualify for CR, PR, or progression. All measurable and evaluable sites must be assessed using the same techniques as baseline. The steroid dose at the time of the scan

Version Date: 07/17/2025 Page 36 of 96

evaluation should be no greater than the maximum dose used in the first 8 weeks from initiation of therapy.

- 6.4.1.4.5 Progression: 25% increase in the sum of products of all measurable lesions over smallest sum observed (over baseline if no decrease) using the same techniques as baseline, OR clear worsening of any evaluable disease, OR appearance of any new lesion/site, OR clear clinical worsening or failure to return for evaluation due to death or deteriorating condition (unless clearly unrelated to this cancer). Patients will also be considered to have progressive disease if there is significant increase in T2/FLAIR non-enhancing lesions AND clinical progression. (See section 6.4.1 and 6.3.7 for definitions). To be considered progressive disease, increase in T2/FLAIR should occur on stable or increasing doses of corticosteroids compared to baseline scan or best response following initiation of therapy, and should not be due to co-morbid events (e.g. radiation therapy, demyelination, ischemic injury, infection, seizures, post-operative changes, or other treatment effects).
- 6.4.1.4.6 Unknown: Progression has not been documented and one or more measurable or evaluable sites have not been assessed.
- 6.4.2 Best Response: This will be calculated from the sequence of objective statuses.

For patients with all disease sites assessed every evaluation period, the best response will be defined as the best objective status as measured according to Section 6.4.1. If the response does not persist at the next regular scheduled MRI, the response will still be recorded based on the prior scan, but will be designated as a non-sustained response. If the response is sustained, e. g. still present on the subsequent MRI, it will be recorded as a sustained response, lasting until the time of tumor progression. Best response is unknown if the patient does not qualify for a best response or increasing disease and if all objective status determinations before progression are unknown.

- 6.4.3 Neurological Exam: Although not used for determining response, it is useful to evaluate improvement in the neurologic exam, (as compared to the baseline assessment), that should coincide with objective measurement of tumor size.
 - +1 Better
 - 0 Unchanged
 - -1 Worse
 - B Baseline

Version Date: 07/17/2025 Page 37 of 96

6.4.4 Performance Status: Patients will be graded according to Karnofsky Performance Status (See Appendix 15.1). Clinical progression can be declared if there is a decrease in 100 or 90 to 70 or less, at least 20 from 80 or less, or decline in KPS from any baseline to 50 or less, for at least 7 days and not attributable to comorbid events or change in steroid dose.

- 6.4.5 Time to Treatment Failure: From date of registration to the date of first observation of progressive disease (as defined in Section 6.4.1.4.5), non-reversible neurologic progression or permanently increased steroid requirement (applies to stable disease only), death due to any cause, or early discontinuation of treatment.
- 6.4.6 Time to Death: From date of registration to date of death due to any cause.
- 6.4.7 Documenting FLAIR: investigators will be asked to measure tumor related changes on FLAIR sequence as best as possible, as non-enhancing patterns of recurrence can occur. If this occurs within the setting of clinical progression not caused by seizures or other identifiable cause, the patient will be considered to have progressive disease. Please see section 6.4.1 for definition of clinical progression.

Presumed non-enhancing tumor without clinical progression should be observed. The time of progression if eventual clinical deterioration occurs can be back dated to the time of the increase in non-enhancing tumor. Investigators will also be asked to document if recurrence of disease is multifocal.

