1 INTRODUCTION

1.1 **OBJECTIVES**

1.1.1 Primary endpoint:

- 6 month progression free survival rate for recurrent glioblastoma (rGBM) patients with no prior bevacizumab exposure treated with pazopanib and topotecan (Group A).
- 3 month progression free survival rate for rGBM patients with prior bevacizumab exposure treated with pazopanib and topotecan (Group B).

1.1.2 Secondary endpoint:

- Overall survival for rGBMs (Group A and Group B) treated with pazopanib and topotecan measured from time of study enrollment.
- Objective response rate for rGBM (Group A and Group B) treated with pazopanib and topotecan.
- Patient related outcome measures.
- To evaluate the occurrence of symptoms and correlate to disease progression and tolerance to treatment using the MD Anderson Symptom Inventory-Brain Tumor Module (MDASI-BT) self-reporting tool. This will include:
 - To evaluate longitudinal changes in symptom measures and determine the impact of the therapy on these parameters.
 - To measure symptom burden over the course of therapy to evaluate differences between patients individual symptom severity, overall mean symptom severity, and difference in scores on the interference items between responders and nonresponders.
 - O To describe the variability of symptom severity longitudinally over the treatment course and follow-up period.

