Recent work has begun to subcategorize GBM into various subgroups based on the primary molecular pathways involved (Phillips et al. 157-73;Brennan et al. e7752). One study of particular relevance to this proposal, using proteomic analysis, identified three patterns of expression and activation of proteins in glioma signaling pathways, one of which was a PDGF-pathway activation which was primarily ligand driven (Brennan et al. e7752). The other pathways were EGFR and NF1. GBM patients were evenly distributed among the three groups, suggesting up to 1/3 of GBM patients would possess the PDGF pathway activation pattern. There was a trend for tumors that had been previously treated to reside in the PDGF group (p=0.11). Interestingly, even though this group of tumors was defined by evidence of PDGF signaling at the protein level, none of the tumors in the class showed gene amplification of either PDGF receptors or ligands. The PDGF pathway analysis included a cluster of 17 proteins including PDGFB, phospho-PDGFRβ, and phospho-NFKB1 as well as others. This PDGF core was felt to most closely resemble the tumors recently described as "pro-neural" (Phillips et al. 157-73).

1.2.2 Pazopanib:

Pazopanib is an oral angiogenesis inhibitor targeting VEGFR, PDGFR, and c-Kit, and was recently FDA approved for advanced renal cell carcinoma. Single-agent Pazopanib at 800 mg daily was tested in a phase 2 study in recurrent GBM and was well tolerated. However, Pazopanib demonstrated a 6-month progression free survival (PFS6) of only 3% (not meeting the efficacy target), a median PFS of 12 weeks, and a median overall survival of 35 weeks. However, Pazopanib did demonstrate biological activity, in that 11 patients (31%) had a PR or a <50% reduction in tumor, indicative of Pazopanib's effect on tumor vasculature (Iwamoto et al. 855-61). Pazopanib (in combination with lapatinib) in relapsed malignant glioma showed a clinical benefit rate (CR + PR + SD > 8 weeks) of 50-68%.

1.2.3 Topotecan:

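### Partial response carries no explicit T2/FLAIR condition, so one scan can be both the best response and the back-dated progression date

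*Combined protocol and SAP*

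**What the plan says.** Objective response is a named secondary endpoint in section 1.1.2: "Objective response rate for rGBM (Group A and Group B) treated with pazopanib and topotecan". PR (6.4.1.4.2) requires a "Greater than or equal to 50% decrease under baseline in the sum of products of perpendicular diameters of all measurable lesions", then "No progression of evaluable disease. No new lesions", assessment by the baseline technique, and a ceiling on the steroid dose. Complete response (CR, 6.4.1.4.1) is stricter: "Complete disappearance of all measurable and evaluable disease. No new lesions. No evidence of non-evaluable disease", and no steroids. Neither definition names T2/FLAIR.

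T2/FLAIR appears under progression. In 6.4.1.4.5 a marked non-enhancing increase counts as progression only when clinical progression is also present, with a steroid condition and a list of excluded causes. Section 6.4.7 adds "Presumed non-enhancing tumor without clinical progression should be observed", and then: "The time of progression if eventual clinical deterioration occurs can be back dated to the time of the increase in non-enhancing tumor".

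For patients with all sites assessed, 6.4.2 states that "the best response will be defined as the best objective status". No confirming scan is needed. A response that is gone at the next MRI stays on record, labelled non-sustained, and a sustained one lasts until progression. Nothing in 6.4.2 deals with a scan that later becomes the progression date.

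**The concern.** The progression rule looks at non-enhancing tumour, but the PR rule does not explicitly do so. A patient whose measurable lesion halves while non-enhancing tumour grows meets the PR wording on that scan. If the patient then deteriorates, the protocol allows that scan to be named as the time of progression, while 6.4.2 keeps it as the best response.

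Two results are at stake. One is the objective response rate in each group. The other is the MDASI-BT analysis (sections 1.1.2 and 9), which compares symptom severity and interference between responders and non-responders and so inherits any misclassification. The setting makes the gap relevant: pazopanib is a VEGFR inhibitor, section 1.2.2 attributes the shrinkage seen with it to an effect on tumour vasculature, and 6.4.7 itself acknowledges that recurrence can be non-enhancing.

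**Working it through.** **1. Score one scan by the text.** Suppose the measurable sum of products is down by at least 50%, T2/FLAIR non-enhancing tumour is clearly larger, there is no new lesion, steroids are within the limit, and the patient is clinically stable.
- CR: not met, because measurable disease remains.
- Progression: the 25% size rule, the new-lesion rule and the clinical rule are not met. The T2/FLAIR route also needs clinical progression, so it is not met. The evaluable-disease route is taken up in step 3.
- PR: every stated condition is met.

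**2. Follow the patient forward.** Group A is scanned before odd-numbered 28-day cycles (3.4.1.2). Take the scan above as the one before cycle 3, at 2 × 28 = 56 days. Suppose clinical progression as defined in 6.4.4 is present at the scan before cycle 5, at 4 × 28 = 112 days. Under 6.4.7 the progression date can be set to day 56. Under 6.4.2 the best response is PR, also on day 56. If the response was still present at day 112 it is called sustained, and its duration to progression is 56 − 56 = 0 days.

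**3. Test the reading that would close the gap.** Evaluable disease (6.4.1.2) includes masses with unclear margins. If non-enhancing tumour belonged there, its growth would block PR.

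| Reading | PR on this scan | Consequence elsewhere |
|---|---|---|
| Non-enhancing tumour is not evaluable disease | Allowed | Consistent with 6.4.1.4.5 and 6.4.7 |
| Non-enhancing tumour is evaluable disease | Blocked | Its clear worsening would be progression by itself under 6.4.1.4.5, against the joint T2/FLAIR-plus-clinical rule in that section and the observation rule in 6.4.7 |

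Only the first reading leaves the T2/FLAIR rules with work to do.

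**4. Test CR.** CR needs all evaluable disease gone and no sign of non-evaluable disease. Growing non-enhancing tumour is hard to reconcile with that, so CR is largely protected. The wording is not clean, because 6.4.1.3 marks non-evaluable disease as not applicable to response evaluation.

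**5. Size.** The plan states no target, hypothesis or denominator for the response rate, so there is no figure of its own to reproduce. Change per reclassified responder = 1/N:
- Full accrual, all patients counted: 1/34 = 2.9 points (Group A); 1/32 = 3.1 points (Group B).
- Stopped after stage 1: 1/9 = 11.1 points; 1/14 = 7.1 points.

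Illustration, assuming 10 recorded responders per group and 0 to 4 of them reclassified: Group A goes from 10/34 = 29.4% to between 29.4% and 6/34 = 17.6%; Group B from 10/32 = 31.25% to between 31.25% and 6/32 = 18.75%. For scale, the exact 95% interval at 10/34 is 15.1% to 47.5%. Neither the 10 nor the 0 to 4 comes from the documents.

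**6. What does not move.** An exact two-stage search under the section 9 inputs returns both stated designs:
- Group A: 9 then 34 patients, at least 2 then at least 9 successes; attained alpha 0.047, power 0.811.
- Group B: 14 then 32 patients, at least 1 then at least 2 successes; attained alpha 0.029, power 0.801.

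Both count progression-free patients. Neither uses response, so the PR wording changes no sample size, error rate or go/no-go rule.

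**The case against.** The strongest reply is that PR is ambiguous rather than silent, because the evaluable-disease condition could be read to cover ill-defined non-enhancing tumour. Step 3 shows that this reading conflicts with two other rules. What stands is that sites could score the same scan differently, which is itself a reason to write the rule down.

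Second, the same-scan outcome needs a long chain: a halved lesion, a significant T2/FLAIR increase on stable or rising steroids with no excluded cause, later clinical decline, and a decision to back-date that 6.4.7 permits but does not require. This stands. It limits the likely frequency, but the text has no rule for when it happens. The nearest is the sentence in 6.4.2 on unknown best response, which mentions status determinations before progression. It says only when best response is unknown and withdraws nothing already recorded.

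Third, response rate is secondary, the symptom comparison is estimation only, and the non-sustained label exposes some of these cases. All of this stands and keeps the point moderate.

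A reader might also infer a false-response rate from section 1.2.2, where "11 patients (31%) had a PR or a <50% reduction in tumor" on single-agent pazopanib is reported beside a 6-month progression-free survival of 3%. The documents do not support that. The 11 patients include reductions too small to be PR, and nothing is said about T2/FLAIR growth; they may have progressed by enhancing growth, new lesions or death.

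**Conclusion.** The point holds for PR. As written, one scan can be recorded as PR, kept as best response, and later serve as the progression date, and no text resolves the conflict. Any resulting error runs one way: it can only raise the objective response rate, by 2.9 points per patient in Group A and 3.1 in Group B. Those figures assume full accrual and every patient in the denominator. The plan defines no response denominator, and 2.1.1.4 admits post-operative patients without measurable disease, so a smaller denominator would make each case count for more.

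Three stronger conclusions should not be drawn. It is not shown that the response rate will be inflated, since the documents establish only the direction of error and not its frequency. CR is not open in the same way, since its own conditions largely exclude visible non-enhancing tumour. The primary progression-free survival decisions are not altered by the PR wording.

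**What to change.** 1. In 6.4.2, state that a scan that is the date of progression, including a date moved back under 6.4.7, cannot count toward best response. By the same logic, scans after that date should not count either. This is needed for coherence even if the second change is declined.
2. In 6.4.1.4.2, add that PR requires no significant growth of T2/FLAIR non-enhancing disease relative to baseline or the best prior scan, under the steroid condition and exclusions already in 6.4.1.4.5. Because CT is permitted (2.1.1.11), flag responses followed by CT only as FLAIR not assessed.
3. While editing, clarify 6.4.1.3 against the CR wording, and repair the cross-references in 6.4.1.4.5: there is no section 6.3.7 (the FLAIR text is in 6.4.7), and clinical progression is defined in 6.4.4.

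Cost: a few sentences. FLAIR measurement is already requested in 6.4.7. A scan that fails the added condition, without progression, would be scored as stable. Stable and responding patients both continue therapy under 3.7.1.2, so no treatment decision changes. The downsides are that the reported response rate may be slightly lower, and that the T2/FLAIR judgement is partly subjective: the measurement is best-effort and the protocol sets no threshold for a significant increase. The fix does not deal with vascular shrinkage when T2/FLAIR is stable; that would still count as PR.
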